5.4 Post-Procedure Data

Post-procedure data will be collected at 24 hours, 7 days, and 30 days, and will be summarized using descriptive statistics (e.g., mean, standard deviation, n, minimum, maximum) for continuous variables and frequency tables for discrete variables.

5.5 Interim Analyses

No formal interim analyses are planned for this study.

5.6 Subgroup Analyses

Stratified analyses will include tabulating the primary and select secondary endpoints by gender.

5.7 Justification of Pooling

The analyses will be performed using data pooled across institutions. An assessment of the poolability of patients across sites will be made by fitting generalized linear models with site as the factor of interest and the primary endpoint as the outcome variable.

5.8 Multivariable Analyses

Multivariable analyses may be performed to identify potential predictors and assess their effect on the primary endpoint.

5.9 Learning Curve Analyses

A generalized linear model will be fit to investigate the effect of time since first enrollment and sites/physicians (and potential interaction between time and sites/physicians) on the primary and select secondary endpoints.

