- If clear fluid is aspirated, this may indicate that the pancreatic duct has been accessed. Re-attempt to access the bile duct. If no fluid is aspirated, or if there is remaining uncertainty over which duct was accessed, physicians if they wish, may use a brief tap on the fluoroscopy pedal to assess whether the guidewire appears to be in the bile duct. Alternatively, they may proceed to an early double wire and/or transpancreatic septotomy cannulation technique. They MUST proceed to double wire and/or transpancreatic septotomy cannulation techniques if fluoroscopy-free cannulation failure persists for 15 minutes. If brief fluoroscopy is used to confirm biliary cannulation, then the case is considered a primary endpoint failure, but the DSC technique for stone evaluation and clearance may be continued. Secondary endpoints will be assessed in these patients, including patient radiation exposure.
- If initial fluoroscopy-free cannulation failure persists for 15 minutes, a double wire and/or transpancreatic septotomy cannulation technique should be attempted.
- If cannulation failure persists despite these advanced cannulation techniques for an additional 15 minutes, this will be considered a **cannulation failure**. The patient will **crossover to the ERC arm** where these cannulation techniques will be continued with full fluoroscopy support. If cannulation in the ERC arm fails despite use of fluoroscopy and basic/advanced cannulation techniques for an additional 15 min then participating institutions may then proceed with their standard of care interventions at this point. Use of needle-knife other than for visibly impacted stones will be considered a cannulation failure for these crossover patients.
- Patients will be followed through 30 days post index procedure as indicated in the follow-up schedule.
- 3. After fluoroscopy-free cannulation succeeds, biliary sphincterotomy will be performed. Additional papillary large balloon dilation can be performed if the sphincterotomy is felt to be inadequate
- 4. The sphincterotome will be exchanged for the SpyGlass cholangioscope over the guidewire.
- 5. The cholangioscope will be advanced into the bile duct up to the bifurcation (hilum) and distance from ampulla to the bifurcation (hilum) will be noted. (Adhesive tapes placed on SpyGlass shaft where it exits the duodenoscope working channel when cholangioscope is at the bifurcation, and again when it just exits ampulla will allow measurement of this distance).

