9.3.6. Justification of Pooling

The analyses will be performed using data pooled across institutions. An assessment of the poolability of patients across sites will be made by fitting generalized linear models with site as the factor of interest and the primary endpoint as the outcome variable.

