9.3.8. Learning Curve Analysis

A generalized linear model will be fit to investigate the effect of time since first enrollment and sites/physicians (and potential interaction between time and sites/physicians) on the primary and select secondary endpoints.

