3.1.1 Hypotheses

We hypothesize that the DSC-guided stone clearance rate is non-inferior to that of the ERC-guided stone clearance rate. We assume a DSC-guided and ERC-guided stone clearance rate of 90% with a 10% non-inferiority margin. The following hypothesis will be tested:

H₀: P_{DSC} minus $P_{ERC} \le -\Delta$ (Inferior) H₁: P_{DSC} minus $P_{ERC} > -\Delta$ (Non-inferior)

where P_{DSC} and P_{ERC} are the stone clearance rates for the DSC arm (test) and the ERC arm (control), respectively, and (Δ delta) is the non-inferiority absolute margin.

Form/Template 90702621 Rev/Ver AE < Non-Complex Biliary Stones RCT, document 92232577, Rev/Ver AA > Page 9 of 13

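### Minor: as described, the learning-curve and pooling models name no treatment arm, so a time trend or site variation in clearance cannot be assigned to DSC or ERC

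*SAP*

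**What the plan says.** The learning-curve analysis in SAP 5.9 fits a model to "investigate the effect of time since first enrollment and sites/physicians (and potential interaction between time and sites/physicians) on the primary" and on some secondary endpoints. SAP 5.7 assesses poolability by "fitting generalized linear models with site as the factor of interest and the primary endpoint as the outcome variable". Protocol 9.3.8 ("A generalized linear model will be fit to investigate the effect of time since first enrollment") and 9.3.6 ("fitting generalized linear models with site as the factor of interest") read the same way.

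The primary hypothesis in SAP 3.1.1 concerns a difference: P_DSC and P_ERC "are the stone clearance rates for the DSC arm (test) and the ERC arm (control), respectively", and the test is on the first minus the second.

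Two other sections could have supplied an arm term, and neither does. SAP 5.8 is optional and lists no variables: "Multivariable analyses may be performed to identify potential predictors and assess their effect on the primary endpoint". SAP 5.6 covers one factor only: "Stratified analyses will include tabulating the primary and select secondary endpoints by gender".

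The two arms do not fail in the same ways. For the DSC arm alone, Protocol 8.6 states: "If brief fluoroscopy is used to confirm biliary cannulation, then the case is considered a primary endpoint failure".

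**The concern.** The roll-in cases in Protocol 5.1 show that operator experience is thought to matter, and the fluoroscopy rule in Protocol 8.6 gives DSC a failure route that ERC does not have. Learning may therefore differ by arm. A model with time and site/physician terms only gives one slope for a mixture of both arms.

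Pooling raises a similar problem. What is pooled across sites for the primary analysis is a DSC-ERC difference, whereas a model on site alone compares overall clearance between sites.

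At stake is how two supportive analyses can be interpreted. A programmer who takes the listed terms literally would produce a slope and a site test that belong to neither arm. Arm terms added after the data are seen would be post hoc.

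**Working it through.** **1. The plan's own figure.** Inputs from SAP 3.1.2: 90% clearance in both arms, margin 10 points, one-sided alpha 0.05, power 80%. The normal approximation gives (1.645 + 0.842)² × (2 × 0.9 × 0.1) / 0.10² = 6.185 × 18 = 111.3, so 112 per arm. The plan specifies an exact test. An exact unconditional test on the score statistic has 81.7% power at 125 per arm, with attained level 0.0495. N = 250 therefore stands, and it does not depend on either model discussed here.

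**2. Learning: what the arm-free slope estimates.** Every rate below is an illustrative assumption, not a figure from the documents. Let β_D and β_E be the logit slopes over experience scaled 0 to 1. With 1:1 allocation the arm-free slope is roughly (β_D + β_E)/2. A rise from 80% to 97% is ln(0.97/0.03) − ln(0.80/0.20) = 3.48 − 1.39 = 2.09. If only DSC rises, the arm-free slope is about 2.09/2 = 1.05; if only ERC rises, it is again about 1.05.

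Simulation: 250 patients, blocks of 4 within site, site intercept logit SD 0.5, site terms in every model, the other arm flat at 90%, two-sided 5% Wald tests, 3,000 trials. Each cell gives the median slope and the rejection rate.

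| Scenario | Arm-free | DSC arm only | Arm-by-experience |
|---|---|---|---|
| DSC rises, 15 sites | 1.06, 28% | 2.50, 49% | 2.33, 28% |
| ERC rises, 15 sites | 1.05, 27% | 0.00, 6% | −2.33, 29% |
| DSC rises, 8 sites | 1.00, 26% | 2.29, 46% | 2.23, 27% |
| ERC rises, 8 sites | 1.00, 25% | −0.02, 5% | −2.27, 28% |

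The DSC-arm slope of 2.50 is biased upward from 2.09 by the fixed site terms.

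For a milder DSC rise (85% to 95%, 2,000 trials) detection is 14%, 22% and 13% respectively. If both arms rise from 80% to 97%, the arm-free model does better than the DSC-arm fit: 78% against 48%.

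This pattern is expected. If v is the variance of a one-arm slope, taken as equal in the two arms, and only DSC improves, the signal-to-noise ratios are:
- arm-free: (β_D/2)/√(v/2) = β_D/√(2v)
- arm-by-experience: β_D/√(2v)
- DSC arm only: β_D/√v

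The interaction term therefore detects no more than the planned model, but it does show which arm changed.

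**3. Pooling: what a site-only test can see.** Suppose only DSC shifts by δ at a site, with n patients per arm and clearance p. The site's overall rate moves by δ/2.
- Site-only ratio: (δ/2)/√(p(1−p)/(2n)) = δ/√(2p(1−p)/n)
- Arm-by-site ratio: δ/√(2p(1−p)/n)

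The two are equal, so similar detection is expected when one arm alone varies. The result is different when both arms move. For example, let one site have DSC 80% and ERC 98%, and another the reverse. Both have (80 + 98)/2 = 89% overall, yet the differences are −18 and +18 points.

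Simulation: 15 sites, 20,000 trials, heterogeneity tests with critical values calibrated at 90% in both arms.

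| Assumed pattern | Site-only rejects | Arm-by-site rejects |
|---|---|---|
| DSC alone varies, logit SD 0.5 | 9.5% | 8.9% |
| DSC alone varies, logit SD 1.0 | 30.1% | 30.6% |
| DSC 15 points lower at alternate sites | 12.2% | 13.1% |
| Case mix only, logit SD 0.5 | 24.4% | 5.3% |
| Case mix only, logit SD 1.0 | 79.7% | 4.1% |
| Difference alternates ±5 points, cancelling | 4.8% | 10.5% |
| Difference alternates ±10 points, cancelling | 4.3% | 33.9% |
| Difference alternates ±15 points, cancelling | 3.0% | 77.9% |

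With 8 sites and DSC alone varying, the figures are 10.7% against 11.1% (SD 0.5) and 35.6% against 37.2% (SD 1.0).

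**4. Precision.** The 95% CI half-width is about 2.4 to 2.5 logits for the DSC-arm slope and 3.2 to 3.3 for arm-by-experience. At 90% clearance, 42% of site-arm cells have no failure with 15 equal sites, and 19% with 8.

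**The case against.** The wording does not forbid an arm term. The pooling section speaks of models in the plural, and its stated aim concerns patients rather than the treatment difference, which a site model partly answers. Randomisation is 1:1 within site, so site main effects do not confound the comparison. All of this stands. It limits the point to what is described and supports keeping the planned models.

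A reader might infer that the site-only check is blind to inconsistency in the DSC-ERC difference, citing 3% against 78%. That contrast arises only when effects run in opposite directions and cancel within each site. When DSC alone varies, the site-only test detects it as often as arm-by-site does.

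On learning, the roll-in cases in Protocol 5.1 come before randomisation and may remove part of early DSC learning. A start at 80% is pessimistic beside the 93% and 90% reported for the two DSC series in the Protocol introduction. Detection also gains little: arm-by-experience matches the arm-free model, and the DSC-arm fit stays below 50% with an interval half-width larger than the assumed slope. These objections stand, so the case for change rests on attribution. The calculations cover the binary primary endpoint only, not the secondary endpoints that SAP 5.9 also mentions.

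**Conclusion.** The point holds as a minor one. As described, neither model names arm, and no other section commits to it. The learning slope is then a mixture, about 1.0 logit whether DSC or ERC is the arm that improves. The site check cannot attribute variation to an arm, can react to case mix that leaves the difference unchanged, and misses effects that cancel within a site.

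These sizes depend on assumed rates, assumed between-site SDs and 8 or 15 equal sites; the documents give none of these beyond 90% clearance and a maximum of 15 sites. The direction of the conclusion follows from the model terms alone.

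A reader might go further and infer that the non-inferiority conclusion is at risk. The documents do not support that: both analyses are supportive, no decision rule is attached to either, and the primary exact test and N = 250 do not use them.

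**What to change.** **SAP 5.9.** Keep the planned all-patient model, which is the better one if both arms improve alike. Add arm and arm-by-experience. Report alongside it a DSC-arm fit on each endoscopist's sequence of randomised cases, with site/endoscopist as a random or penalised term to limit the bias from fixed site terms. Give estimates with confidence intervals. Also state the time origin: enrolment occurs at consent (Protocol 8.3), and the text does not say whether the first enrolment is the trial's or the site's, or a roll-in or a randomised case. This is only a wording gap.

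**SAP 5.7.** Keep the site model. Add arm and arm-by-site, with site random or small sites combined. Report the variation in the DSC-ERC difference descriptively, with no pass/fail test. Align Protocol 9.3.6 and 9.3.8.

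**Cost.** SAP wording and a few lines of code for randomised cases, through the amendment route in SAP 5.10 before the analyses are performed. The estimates will be imprecise, as shown above. Roll-in cases should enter only if their procedural data and operator are recorded: Protocol 8.7 includes them expressly for follow-up, but the procedural list in 8.6 names neither roll-ins nor the operator. Site and endoscopist should largely coincide, since SAP 1 reserves procedures for the Principal Investigator apart from exceptions.

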2.2. SpyGlassTM DS Digital Controller

The SpyGlassTM DS Digital Controller is an electronic device that: receives video signals from a SpyScope DS Catheter, processes the video signals and outputs video images to a video monitor. The controller also generates and controls the light transmitted to the tip of the SpyScope DS Catheter to illuminate the area of interest within the anatomy. Buttons on the controller's front panel enable you to control the brightness level of the light.

To use the controller, connect it to a video monitor with a video cable and then connect a SpyScope DS Catheter to the controller. The controller provides direct visualization of the pancreatico-biliary duct anatomy and enables exploratory and endotherapy procedures.

The following devices will be available for use upon commercialization.

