Number of Subjects	 250 subjects An additional 5 Roll-in cases. Each participating endoscopist at each of the participating centers must perform up to 5 Roll-in cases. These roll-in cases will not count towards enrollment ceiling of 250 cases. Procedures to be conducted only by the Principal Investigator. Sub-Investigators will be authorized to do study procedures only on an exception basis. Such exception may be granted by the Sponsor in consultation with the Principal Investigator of the site and Lead Principal Investigator to the study. 	
Number of Sites	Up to 15 global sites	
Primary Endpoint	Complete stone clearance by extraction of bile duct stones from the common bile duct (CBD) into duodenum as determined by fluoroscopy free cholangioscopy in the DSC arm and by cholangiography in the ERC arm.	
Secondary Endpoints	1. Evaluation of all serious adverse events (SAEs) including all deaths (related and unrelated), severity, onset, time to resolution related to the DSC devices and/or procedure and/or the ERC procedure through 30 days post procedure.	
	2. Radiation exposure to the patient (total fluoroscopy time, total radiation dose, Dose Area Product (DAP), effective dose), from duodenoscope in to completion of stone clearance, not including the validation DSC procedure in ERC arm and ERC procedure in DSC arm.	
	 Duration of procedure defined as time from duodenoscope in to completion of stone clearance, not including the validation DSC procedure in ERC arm and ERC procedure in DSC arm. 	
Follow-up Schedule	 Telephone follow-up during the following post-procedure intervals: 24 hours 7 days 	

E7131 – Non-Complex Biliary Stones DSC vs ERC RCT			
	• 30 days		
Study duration	Approximately 2 years		
Inclusion Criteria	 18 years or older Abdominal pain consistent with choledocholithiasis (procedure possible within 72 hours of onset of symptoms and imaging suggesting choledocholithiasis, contingent on persistent abdominal pain) Abnormal LFTs 		
	 4. Non-complex biliary stone disease, defined as 5 or fewer stones in the common bile or common hepatic duct with largest stone no larger than 10 mm in size. If stones not seen on imaging (US, CT) the bile duct diameter should be ≤12 mm* 		
	* Given the poor sensitivity (approximately 20%) for biliary stones of CT and US, the diameter of the dilated CBD is used as a surrogate for largest stone diameter		

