3.1.2 Sample Size

The sample size was estimated based on the following assumptions:

- Expected stone clearance rate of 90% in DSC-guided and ERC-guided group
- Non-inferiority margin: 10%
- Alpha (1-sided): 0.05
- Power: 80%

With the above assumptions, a sample of 250 patients (125 in each arm) is needed to detect the non-inferiority of the clearance rate in the DSC arm compared to the ERC arm. This sample size was calculated using StatXact 9[®].

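### The learning-curve model measures experience by elapsed time, with no arm or device term, and with many sites its fixed site and site-by-time terms are not reliably estimable for the primary endpoint

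*SAP*

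**What the plan says.** SAP 5.9 plans a generalized linear model to investigate the "effect of time since first enrollment and sites/physicians (and potential interaction between time and sites/physicians"). The outcomes are given by "on the primary and select secondary endpoints". Protocol 9.3.8 has the same text. Neither section says whether the time origin is the first enrolment in the trial, at the site or by the physician. Neither names a case-sequence, arm or device term, or a method for sparse data.

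The related provisions are:

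- **Sites and operators (SAP 1):** "Up to 15 global sites", and "Procedures to be conducted only by the Principal Investigator", with exceptions granted by the sponsor. Site is therefore close to operator.
- **Size (SAP 3.1.2):** "a sample of 250 patients (125 in each arm) is needed to detect the non-inferiority", at an expected clearance of 90% in both arms.
- **Roll-ins (SAP 1, Protocol 5.1):** up to 5 per endoscopist, before randomization and outside the 250. The protocol synopsis says 5.
- **Validation (Protocol 8.6, Group A, step 9):** ERC-arm patients judged clear then undergo cholangioscopy.
- **Devices (Protocol 2.2):** "The following devices will be available for use upon commercialization". This covers the DS II catheter and the Retrieval Basket, with no date.
- **Poolability (SAP 5.7):** assessed by "fitting generalized linear models with site as the factor of interest and the primary endpoint as the outcome variable".

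**The concern.** A learning curve relates outcome to the number of procedures an operator has done. Elapsed time stands in for that number only as far as operators accrue cases at similar rates. It gives no credit for roll-ins, and it does not register how many validation cholangioscopies were done.

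The outcome also differs by arm. In the DSC arm, brief fluoroscopy to confirm cannulation counts as a primary-endpoint failure (Protocol 8.6, Group B, step 2). The ERC arm has no such rule. A model without an arm term dilutes any DSC learning with ERC cases.

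The second issue is sparsity. With few failures spread over many sites, some sites will have none, or will have all their failures before or after all their successes. Ordinary maximum likelihood then gives infinite estimates for those sites. At stake is a planned exploratory analysis that could report unusable site and interaction effects, and a time effect that is hard to read as learning.

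**Working it through.** **Plan's own figure.** Inputs from SAP 3.1.2: 90% v 90%, margin 10%, one-sided alpha 0.05, power 80%. The unpooled normal approximation gives (1.645 + 0.842)² × (0.09 + 0.09) / 0.10² = 111.3, so 112 per arm (224 in total). The plan specifies an exact test. An exact unconditional test ordered by the Farrington-Manning score gives size 0.0495 and power 81.7% at 125 per arm. The stated 250 is therefore reproduced under the exact method.

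**Expected failures.** 250 × 0.10 = 25, or 12.5 per arm. The total would be 37.5 at 85% clearance and 12.5 at 95%.

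**Parameters with S sites (logistic link assumed).** Intercept and site dummies take S, a common time slope 1, and the interaction S − 1, which totals 2S. Without the interaction the total is S + 1. At S = 15 these are 15 + 1 + 14 = 30, and 16.

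**Sites with no failure (equal site sizes assumed).** The chance for one site is 0.9^(250/S). At S = 15 this is 0.9^16.67 = 0.173. The expected number of such sites is 15 × 0.173 = 2.6, and the chance of at least one is 1 − (1 − 0.173)^15 = 94%.

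**Infinite estimates in the interaction model.** From 2,000 simulated trials with equal sites and a constant 10% failure rate, a trial is counted if any site has no failures, or if its failures and successes are fully separated in time.

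| Sites | Parameters with / without interaction | Failures per non-intercept parameter | At least one site with no failure | At least one infinite site estimate |
|---|---|---|---|---|
| 15 | 30 / 16 | 25/29 = 0.86; 25/15 = 1.67 | 94% | 97% |
| 10 | 20 / 11 | 25/19 = 1.32; 25/10 = 2.5 | 53% | 62% |
| 5 | 10 / 6 | 25/9 = 2.8; 25/5 = 5.0 | 2.6% | 4% |

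With unequal sites (Dirichlet weights, an assumption) the last column becomes about 100%, 94% and 36%. For the DSC arm alone with equal sites it is 100%, 99% and 37%. A separate run of 4,000 trials with random site sizes found all site estimates finite in 1.9% of trials at 15 sites, 34% at 10 and 65% at 8.

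**What stays estimable.** A common time slope can be estimated even when site terms diverge, but with low power. If failure falls from 15% to 5% over enrolment (illustrative, 300 runs, 15 sites), power is 34% without site terms and 37% with 14 site dummies. The simulation standard error is √(0.35 × 0.65 / 300) ≈ 2.8 percentage points, so the two do not differ.

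**Time as a proxy.** With 15 sites of 17 cases and staggered starts (assumptions), within-site case order correlates about 0.89 with time in the trial and 0.90 with time at the site.

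**Cholangioscopies outside the DSC arm.** ERC-arm validation adds about 125 × 0.90 = 112 at the planned clearance rate. Roll-ins add up to 15 × 5 = 75, taking one endoscopist per site and assuming that roll-ins are DSC cases. The DSC arm itself supplies 125.

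**The case against.** The strongest reply is that the plan is less rigid than a worst-case reading makes it. Fifteen sites is a ceiling and the interaction is only a possibility. With 5 equal sites infinite estimates are rare. The model also covers secondary endpoints, and procedure duration is continuous with up to 250 observations, so it has no separation problem. Site is nearly operator, and case order tracks time closely under the assumptions above. For poolability, a site with no failures has an infinite coefficient, yet the overall likelihood-ratio test for site stays finite, though its chi-square approximation is poor with sparse data. SAP 5.10 allows a documented amendment before analysis. All of this stands, and it makes the point conditional and minor.

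Several stronger readings are tempting, and the documents do not support them:

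- **The model uses calendar time.** The origin is undefined and could be the site's or the physician's own first case. Enrolment means signing consent (SAP 4.1.1), so it is also unclear whether a roll-in could set the origin.
- **Device change confounds the time trend.** No launch date is given. It could fall before, during or after enrolment.
- **The model cannot be fitted, or does not measure learning.** The difficulty is confined to site and interaction terms for the binary endpoint. Time measures experience imperfectly, which is not the same as failing to measure it.
- **The trial will fail to say how many cases an endoscopist needs.** No objective or endpoint asks this.

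The reply leaves two things unanswered. The plan has no term for arm or case number, and it gives no sparse-data method if many sites are used.

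**Conclusion.** The point holds as a minor, conditional improvement. Elapsed time from an undefined origin is an imperfect measure of operator experience, and the model does not separate the arms. With many sites, fixed site and site-by-time terms for the primary endpoint would not be reliably estimable: about 97% of simulated trials have at least one infinite site estimate at 15 sites, about 60% at 10 and 3-4% at 5. These figures assume 90% clearance, equal sites, a logistic model and the full interaction. Unequal sites make them worse. Device change adds a further ambiguity only if a new catheter or basket enters use during enrolment.

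A reader might infer that the primary result is at risk. It is not, because the exact non-inferiority test in SAP 3.1.3 does not use this model.

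**What to change.** Amend SAP 5.9 and Protocol 9.3.8:

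1. Replace time with the endoscopist's cumulative cholangioscopy case number, counting roll-ins. Validation cholangioscopies follow an ERC clearance and are not full DSC extractions, so either count them or show them in a sensitivity analysis.
2. Include arm and arm-by-experience terms, or fit the DSC arm alone and accept about 12.5 expected failures.
3. For the primary endpoint, use a random site/endoscopist effect or Firth penalised logistic regression, with one common slope and no fixed site-by-time interaction. With a random effect, experience, arm and their product are 3 fixed terms, or 25/3 = 8.3 expected failures each.
4. Add a device-version or basket term as a sensitivity analysis only if devices change during enrolment. It would then be correlated with case number.
5. In SAP 5.7, use the same random-site approach or an exact test for poolability.

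The cost is SAP wording, slightly more analysis work and deriving case order from procedure dates. Two data points need confirming. Protocol 8.7 names roll-ins for follow-up data but 8.6 does not name them for procedural data. The device accountability records in Protocol 13 hold device identification, use dates and subject identification, but are not described as part of the analysis database. The analysis remains exploratory, with low power for the binary endpoint.
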